13.4. Appendix 4: Study Phases and Treatment Emergent Adverse Events

13.4.1. Study Phases

AEs will be assigned to study phases as defined in Table 6. Laboratory data (efficacy, safety, and virology), HIV associated Conditions, health outcomes assessments, vital signs, and ECGs will be assigned to study phases as defined in Table 7.

Assessments/events are assigned to study phases sequentially, starting from the top of each table.

Table 6 Study Phases for AEs

Study Phase	Definition
Screen	Date < Intervention Phase Treatment Start Date
Intervention	
For subjects continuing into the Extension Phase: Intervention Phase Treatment Start Date \leq Date < Date of Nominal Month 13 Visit
 
For subjects not continuing into the Extension Phase: Intervention Phase Treatment Start Date \leq Date < LTFU ART Start Date [a]
 
For AEs leading to treatment withdrawal with start date equal to the LTFU ART Start Date, Intervention Phase instead of Long-term Follow-up Phase will be assigned.

Extension Phase	
Date of Nominal Month 13 Visit \leq Date < LTFU ART Start Date [a]
 
For AEs leading to treatment withdrawal with start date equal to the LTFU ART Start Date, Extension Phase instead of Long-Term Follow-up Phase will be assigned.

Long Term Follow-Up	
For subjects who receive at least one CAB/RPV injection and permanently discontinue study treatment: AE Start Date \geq LTFU ART Start Date
 
AEs with completely missing start date:
 
 • If AE end date is \leq Intervention Phase Treatment Start Date, then assign to Screening Phase; • Else if AE end date is completely missing or Intervention Phase Treatment Start Date $<$ AE end date \leq Date of Nominal Month 13 Visit, then assign to Intervention Phase; • Else if AE end date $>$ Date of Nominal Month 13 Visit, then assign to Extension Phase.

Date=AE Start Date

- [a] If participants have missing LFTU ART start date, only the lower bound will be considered in the derivation.

Table 7 Study Phases for Laboratory, PK, ECG, Vital Signs, HIV-1 Associated Conditions, and Protocol Deviation Data

Study Phase	Definition
Screen	Date ≤ Study Treatment Start Date
Intervention	
For subjects continuing into the Extension Phase: Intervention Phase Treatment Start Date < Date < Date of Nominal Month 13 Visit
 
For subjects not continuing into the Extension Phase: Intervention Phase Treatment Start Date < Date ≤ LTFU ART Start Date ^[a]

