Concomitant during Intervention Phase	
For subjects continuing into Extension Phase: Intervention Treatment Start Date^[a] ≤ Medication Taken < Date of Nominal Month 13 Visit
 
For subjects not continuing into Extension Phase^[b]: Intervention Treatment Start Date^[a] ≤ Medication Taken < LTFU ART Start Date

Concomitant during Extension Phase	For subjects continuing into Extension Phase^[b]: Date of Nominal Month 13 Visit ≤ Medication Taken < LTFU ART Start Date
Received during Long-term Follow-up	For subjects who received at least one CAB and/or RPV injection and have started LTFU ART: Medication Taken ≥ LTFU ART Start Date

NOTES:

- Please refer to Appendix 7: Reporting Standards for Missing Data for handling of missing and partial dates for medications. Use the rules in this table if medication date is completely missing.
 - a. The ART medication stopped on start date of Intervention treatment will be considered a prior medication and will not be considered concomitant during the Intervention phase. If the stop date of ART medication is completely missing and this medication is recorded in eCRF as prior, it will be considered a prior medication and will not be considered concomitant during the intervention phase.
 - b. If subjects have missing LFTU ART start date, only the lower bound will be considered in the derivation.

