13.7.2.1. Handling of Missing and Partial Dates

Element	Reporting Detail		
General	
 Partial dates will be displayed as captured in participant listing displays. Where necessary, display macros may impute dates as temporary variables for sorting data in listings only. In addition, partial dates may be imputed for ‘slotting’ data to study phases or for specific analysis purposes as outlined below. 		
Adverse Events	
 Imputations in the adverse events dataset are used for slotting events to the appropriate study time periods and for sorting in data listings. Partial dates for AEs recorded in the CRF will be imputed using the following conventions: 
 
 Missing start day	 
 If study treatment start date is missing (i.e. participant did not start study treatment), then set start date = 1st of month. Else if study treatment start date is not missing: 
 If month and year of start date = month and year of study treatment start date, then 	
 
 	Missing start day	
 If study treatment start date is missing (i.e. participant did not start study treatment), then set start date = 1st of month. Else if study treatment start date is not missing: 
 If month and year of start date = month and year of study treatment start date, then
Missing start day	
 If study treatment start date is missing (i.e. participant did not start study treatment), then set start date = 1st of month. Else if study treatment start date is not missing: 
 If month and year of start date = month and year of study treatment start date, then 		

Element	Reporting Detail			
		
 ▪ If stop date contains a full date and stop date is earlier than study treatment start date, then set start date = 1st of month. ▪ Else set start date = study treatment start date. ○ Else 
 ▪ For Non-ISR AEs: set start date = 1st of month ▪ For ISR AEs: if oral bridging taken during the month and year, set start date = min(last day of the month, day of AE stop date if available, day of study treatment discontinuation if occurring during the month and year); else set start date = 1st of month. 		

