	
 ▪ If stop date contains a full date and stop date is earlier than study treatment start date, then set start date= 1st of month. ▪ Else set start date = study treatment start date. 
 ○ Else set start date = 1st of month. 
Missing start day and month
 
 • If study treatment start date is missing (i.e. participant did not start study treatment), then set start date = January 1. • Else if study treatment start date is not missing: 
 ○ If year of start date = year of study treatment start date, then 
 ▪ If stop date contains a full date and stop date is earlier than study treatment start date, then set start date = January 1. ▪ Else set start date = study treatment start date. • Else set start date = January 1. 
Missing end day
 
A '28/29/30/31' will be used for the day (dependent on the month and year)
 
Missing end day and month
 
A '31' will be used for the day and 'Dec' will be used for the month.
 
Completely missing start/end date
 
No imputation
 
 • The recorded partial date will be displayed in listings. 
ART Medications
 
 • Partial dates recorded in the eCRF will be imputed using the following convention: 
 ○ If the partial date is a start date, a '01' will be used for the day and 'Jan' will be used for the month. ○ If the partial date is a stop date, a '28/29/30/31' will be used for the day (dependent on the month and year) and 'Dec' will be used for the month. • If medications recorded in the PRIOR ART form of the eCRF, then the earlier date of the imputed and the day prior to the Intervention phase treatment start date will be used, i.e. min (imputed stop date, Intervention phase treatment start date - 1). • For medications with completely missing start date, they will be considered started prior to the Intervention phase treatment start date. • For medications with completely missing stop date, they will be considered ongoing unless recorded in the PRIOR ART form of the eCRF. • For ART booster medications, the start and stop dates are not recorded in the database (i.e. missing), the dates will be imputed to be the same as the dates of their parent medications. • The recorded partial or missing date will be displayed in listings.

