13.9. Appendix 9: Snapshot Algorithm Details

Detailed Algorithm Steps

 Consider an analysis visit window for Month X as defined in Table 2. The HIV-1 RNA threshold of 50 will be analysed, in this study The COVID-19 pandemic presents significant logistical challenges for many clinical sites around the world, with variable restrictions being placed on site resources and operations, and on an individual participants ability to attend clinic visits. The snapshot algorithm is modified to allow for the presentation of full scope of COVID-19 relatedness. The analysis window for 'Month 12' and HIV-1 RNA threshold of '50 c/mL' are used for the purpose of illustration. A participant's Snapshot response and reason at Month 12 are categorized as below. 
 HIV-1 RNA < 50 c/mL HIV-1 RNA \geq 50 c/mL 
 Data in window not below 50 
 Non-COVID-19 related 
 Discontinued for lack of efficacy Discontinued for other reason while not below 50 COVID-19 related 
 Discontinued for lack of efficacy Discontinued for other reason while not below 50 No Virologic Data at Month 12 Window 
 Non-COVID-19 related 
 Discontinued study due to AE or death Discontinued study for other reasons On study but missing data in window COVID-19 related 
 Discontinued study due to AE or death Discontinued study for other reasons On study but missing data in window Change in background therapy*

* Note: Use of CAB + RPV oral bridging and SOC oral bridging medication, where the latter is due to unavailability of CAB/RPV IM injections or oral CAB+RPV during the pandemic, will not be considered a "Change in background therapy" in the Snapshot algorithm. All other permanent changes in ART are not permitted in this protocol.

- The steps in determining response and reasons are indicated in the table below, in the order stated.
- Background therapy is not given to participants while on study. The “change in background therapy” in detailed steps below refers to the “change in ART” in this study.

Detailed steps		
Condition ('Month 12' indicates Month 12 window)	Response	Reasons
1. If non-permitted change in background therapy prior to Month 12	HIV-1 RNA \geq 50	Change in background therapy

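### A long-term follow-up ART start known only to the year is imputed as 1 January with no bound at the last study dose, so on-treatment data can be reclassified as post-treatment

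*SAP*

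**What the plan says.** The ART Medications block of SAP 13.7.2.1 gives this rule for start dates: "If the partial date is a start date, a '01' will be used for the day and 'Jan' will be used for the month". The only bound in that block applies to stop dates of medications on the PRIOR ART form. For dates with nothing recorded it adds: "For medications with completely missing start date, they will be considered started prior to the Intervention phase treatment start date".

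The General row of the same table says that partial dates may be imputed to slot "data to study phases or for specific analysis purposes as outlined below". The notes to Table 9 (13.4.1) point the same way: "Please refer to Appendix 7: Reporting Standards for Missing Data for handling of missing and partial dates for medications".

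LTFU ART Start Date ends the Intervention Phase (participants not continuing) or the Extension Phase, and opens LTFU, in Tables 6, 7 and 9. Table 10 (13.4.2) makes everything in LTFU Post-Treatment. Tables 6 and 7 carry a safeguard for one case only: "If participants have missing LFTU ART start date, only the lower bound will be considered in the derivation". Table 9 has an equivalent note.

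Section 13.6.3 bases the Snapshot result on the last on-treatment Intervention Phase value in the window. In Appendix 9 (13.9), step 1 reads "If non-permitted change in background therapy prior to Month 12" and leads to HIV-1 RNA ≥50. Step 3.2.1 also uses LTFU ART Start Date.

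**The concern.** Dating a pre-study regimen back to 1 January does little harm, because it began before study treatment anyway. LTFU ART is different. It follows the last study dose, and its start date is the boundary between treatment and follow-up. An early imputed date describes someone who was already on replacement ART while still receiving injections.

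The effect then runs through the phase tables. Laboratory values and AEs after the imputed date become LTFU and Post-Treatment, and they leave the safety displays, which by SAP section 8 cover the combined Intervention and Extension phases. A Month 12 viral load can also lose its on-treatment status and with it the Snapshot classification shown in efficacy Tables 2.1 and 2.2. The lower-bound footnotes do not help, since a year-only date is partial, not missing.

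**Working it through.** The plan states no figure to reproduce. The check traces one record through the rules and then asks how often the imputed date precedes the last injection.

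**Worked example (assumed dates, participant not entering the Extension Phase)**

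- Oral lead-in starts 15 Aug 2019; Month 1 injection 14 Sep 2019.
- Month 12 visit, last injection and viral load below 50 c/mL: 14 Aug 2020.
- Month 12 window (Table 2, ±42 days): 3 Jul to 25 Sep 2020.
- True LTFU ART start 14 Sep 2020, recorded only as 2020.

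*True date.* The viral load of 14 Aug is not after 14 Sep, so Table 7 gives Intervention. It is also not after last injection + 35 days (18 Sep), so Table 10 gives On-treatment. Result: below 50.

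*Rule as written.* ART start becomes 1 Jan 2020, which is 31+29+31+30+31+30+31+13 = 226 days before the last injection. The viral load falls after it and is LTFU, Post-Treatment. No on-treatment value remains in the window. Two outcomes are then possible:

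- If LTFU ART is read as a non-permitted ART change, 1 Jan precedes the window (3 Jul) and step 1 gives HIV-1 RNA ≥50.
- If not, step 3.2.1 does not apply, because the window's upper bound (25 Sep) is not before min[18 Sep, 1 Jan] = 1 Jan 2020. Step 3.2.2 gives No virologic data for a safety withdrawal, or for another withdrawal whose last remaining on-treatment value was below 50.

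*With a floor at the day after the last dose.* max(1 Jan 2020, 15 Aug 2020) = 15 Aug 2020. The viral load of 14 Aug stays Intervention, On-treatment, and the result is below 50.

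Size per participant: 1/115 = 0.87 percentage points (N=115 from SAP 2.3).

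**How often 1 January precedes the last injection**

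Let the true ART start fall on each day of a 365-day year, g days after the last injection. 1 January is on or before the last injection exactly when both dates share a calendar year, so the share is (365 − g)/365:

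| Gap g (days, assumed) | Share |
|---|---|
| 7 | 358/365 = 98% |
| 14 | 351/365 = 96% |
| 28 | 337/365 = 92% |
| 35 | 330/365 = 90% |
| 60 | 305/365 = 84% |

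With 11 months on treatment, 1 January falls inside the treatment period in 84% to 92% of cases. With 6 months it does so in 50% and with 3 months in 25%. In most of the remaining short-exposure cases it falls before treatment began, which leaves a non-extension participant no Intervention Phase data at all.

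**Extension participants.** Their Intervention Phase runs to the Month 13 visit (Tables 6 and 7), and note b to Table 10 keeps those data On-treatment. The Month 12 viral load therefore keeps its phase. Extension data after an early imputed date are lost. Step 1 could still be triggered, again only if LTFU ART counts as a non-permitted change.

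**The case against.** The trigger is narrow. It needs permanent discontinuation, an LTFU ART start known only to the year and, in practice, the same calendar year as the last dose. The LTFU schedule (13.2.1.3) has HAART dispensed at study visits and its timing discussed with the medical monitor beforehand. Cleaning precedes database freeze (3.2). The outcomes are secondary and descriptive. All of this stands and limits the size. It does not correct the rule for a date that stays partial. The SAP also does not say outright that LTFU ART Start Date is taken from imputed dates, but it offers no other rule for a partial one.

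Five stronger readings are tempting and are not supported:

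- *The non-ART rule would have prevented this.* Its floor, "Else set start date = study treatment start date", applies only when the recorded year (or month and year) matches that of treatment start. Otherwise a year-only date becomes 1 January. In the example it also gives 1 Jan 2020.
- *A known month is overwritten by January.* The parallel stop-date rule chooses the last day according to month and year, which would be pointless if December always replaced the month. Filling in only missing parts is the better reading, and a day-only gap then moves the date by at most 30 days.
- *The participant definitely becomes a virologic failure.* The SAP does not say that ART after permanent discontinuation is a non-permitted change, and withdrawals have their own branch (step 3.2.2).
- *Standard-of-care oral bridging is affected too.* On-treatment status uses the last bridging dose, and pandemic-related bridging is exempt in Appendix 9. A bridging start moves no phase boundary.
- *The rule for completely missing starts flatly contradicts the footnotes.* One classifies medication records; the other handles a missing boundary date. Table 9 also directs completely missing dates to its own rules. The two can be reconciled, though the ART block does not say so.

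**Conclusion.** The concern holds for year-only LTFU ART starts. As written, the rule can place the start of replacement ART before the last injection and so move genuine on-treatment laboratory values and AEs into a Post-Treatment phase. For a participant who did not enter the Extension Phase, it can also remove a valid Month 12 viral load from the Snapshot, at 0.87 percentage points per participant. Whether the result is No virologic data or HIV-1 RNA ≥50 depends on a reading that the SAP leaves open.

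This assumes that partial LTFU ART dates are imputed under 13.7.2.1, as Table 9 directs, and that the true start shares a calendar year with the last dose. The number of such records is unknown and probably small. The point is worth correcting because the stated rule gives a wrong answer when it applies and the repair is simple.

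**What to change.** In the ART Medications block of 13.7.2.1:

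1. Limit the 1 January rule, and the rule that a completely missing start counts as prior, to records on the PRIOR ART form.
2. For LTFU ART, impute only the missing components, then take the later of that date and the day after the last study-treatment dose. The day after is preferable to the dose date itself because Table 6 assigns AEs to the Intervention Phase only if they start strictly before LTFU ART.
3. For a completely missing LTFU ART start, state that the lower-bound-only footnotes of Tables 6, 7 and 9 apply.

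The cost is a few sentences and a small change to the date-imputation code. The downside is that, when the floor applies, the imputed date is the earliest plausible LTFU ART start, not the latest. Data between that date and the true start would still be assigned to LTFU, even where they fall within 35 days of the last injection.

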13.4.2. Treatment State

Within each study phase (based on assignment of study phase described in Section 13.4.1), only those events/assessments which occur within the ranges shown in Table 10 will be considered ‘on-treatment’ for the given phase. No treatment states will be assigned to medications.

For adverse events, partial AE start date will use imputation as described in 13.7.2.1.

Table 10 Treatment State within Study Phases

Study Phase	State	Definition
Screen	Pre-Treatment	All assessments/events within phase
Intervention/Extension	On-treatment	Date \leq max (Date of Last CAB LA +RPV LA IM Dose + 35, Date of Last Dose of Oral Study Treatment (CAB+RPV or SOC Bridging) +1)
	Post-Treatment	Date $>$ max (Date of Last CAB LA +RPV LA IM Dose + 35, Date of Last Dose of Oral Study Treatment (CAB+RPV or SOC Bridging) +1)
Long Term Follow-Up	Post-Treatment	All assessments/events within phase

NOTES:

- Date = Assessment/Start Date
- a. Treatment State is determined after data has been assigned to the study phases as defined in Section 13.4.1.
- b. Last injection and/or last dose of oral study treatment (CAB+RPV or SOC bridging) are only applied to participants who permanently discontinued the study treatment. The assessments for participants who did not permanently discontinue the study treatment will be considered 'On-treatment'. For participants continuing into extension phase, all data assigned to intervention phase per Section 13.4.1 will be considered 'On-treatment'

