
 The Study Day of an event (e.g., lab assessment, vital sign, ECG, start date of AE or HIV associated condition) will be derived as the number of days between the date of the event and the Intervention Phase treatment start date as follows: 
 If date of event \geq start date of study treatment, then 
 Study Day = Date of Event - Intervention Phase Treatment Start Date + 1 If date of event $<$ start date of study treatment, then 
 Study Day = Date of Event - Intervention Phase Treatment Start Date Note that the start date of intervention phase study treatment is on Study Day 1 and the day before this is Study Day -1; i.e., there is no Study Day 0.
Long Term Follow-up Study Day

 The Long-Term Follow Up (LTFU) Study Day of an event (e.g., lab assessment, start date of AE or HIV associated condition) will be derived as the number of days between the date of the event and the end of IP treatment [i.e. max(Last IM Injection Date, Last Oral Bridging End Date)] as follows: 
 If the date of event falls in Long-term Follow up phase, then 
 LTFU Study Day = Date of event - End date of IP + 1
Study Treatment

 Refers to CAB+RPV oral lead-in, CAB + RPV oral bridging, SOC oral bridging, CAB LA + RPV LA

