
 Timeliness of Injections relative to Date of Projected Dosing Visits are assessed by using "actual injection visit date - projected visit date from first injection". The injections of interest in adherence analysis are those after first injection at Month 1. (. Each injection visit is counted only once. Individual CAB and RPV injections administered at the same visit are not counted twice. "Extra" unscheduled injections are excluded from all derivations. For example, if during a scheduled visit a participant receives 1 ml of injection instead of 2 ml due to a dosing error, but this participant returns one week later for the remaining 1 ml injection, then the additional visit is excluded. If a participant receives an extra injection at an unscheduled visit by mistake, this visit will also be excluded. The categories of Timeliness of Injections relative to Date of Projected Dosing Visits are listed below: 
 < -14 days -14 to -8 days -7 to 1

Demographics	

 • 0 • 1 to 7 days • 8 to 14 days • >14 days • Missed Injection without Oral Bridging (COVID-19 related) • Missed Injection without Oral Bridging (Non COVID-19 related) • Missed Injection with Oral Bridging (COVID-19 related) • Missed Injection with Oral Bridging (non COVID-19 related) 	

 • Injection visits are expected monthly from Month 2 until the nominal month of a participant's last injection visit during the phase(s) of interest. For example: 
 • If a participant discontinues study treatment with last injection visit occurring at nominal visit Month 6 (without oral bridging), then injection visits are expected at Month 2, Month 3, Month 4, Month 5 and Month 6. • Missed injections occurring during periods of on-going oral bridging (e.g. oral bridging is ongoing at the time of the data analysis cutoff or participant discontinues study treatment where last study treatment received is oral bridging) are not considered to be expected visits. 	
Site Type	

 • AIDS Healthcare Foundation (Site Id.= PPD) • Federally Qualified Health Center (Site Id.= PPD) • Health Maintenance Organization (Site Id.= PPD) • Private Practice (Site Id.= PPD) • University (Site Id.= PPD) 	

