For Intervention Phase: 
 Exposure to CAB+RPV Oral Lead-in = IP (oral lead-in) stop date - IP (oral lead-in) start date +1 Exposure to CAB LA + RPV LA = Number of IP injection visits received during the Intervention Phase (up to but not including injections administered at Month 13) Exposure to SOC oral bridging: Duration of the SOC ART medication taken as oral bridging during the Intervention Phase. If the SOC oral bridging is taken in different periods during the Intervention Phase, the duration will be calculated by the sum of non-overlapped periods. Exposure to CAB+RPV Oral Bridging (COVID-19 Related): Duration of the CAB+RPV taken as oral bridging for reasons related to COVID-19 during the Intervention Phase. If COVID-19 related CAB+RPV oral bridging is taken in different periods during the Intervention Phase, the duration will be calculated by the sum of the non-overlapped periods. Exposure to CAB+RPV Oral Bridging (Non COVID-19 Related): Duration of the CAB+RPV taken as oral bridging for reasons not related to COVID-19 during the Intervention Phase. If non COVID-19 related CAB+RPV oral bridging is taken in different periods during the Intervention Phase, the duration will be calculated by the sum of the non-overlapped periods. Overall Exposure to Study Treatment: min [Date of Latest Intervention Phase Visit up to and including Month 13, max (Date of Last Injection + 35, Date of Last Dose of Oral CAB+RPV, Date of Last Dose of SOC Oral Bridging)] – min (Start Date for Oral lead-in CAB+RPV, Date of First CAB/RPV Injection) + 1 
 Note: Conditions in the above formula pertaining to Last Injection/Last Dose of Oral CAB+RPV/Last Dose of SOC Oral Bridging are only applicable to those who permanently discontinued study treatment. 	

Other Safety Endpoints	

 • Overall Exposure to CAB + RPV = Overall Exposure to Study Treatment – Exposure to SOC Oral Bridging 	
For Intervention + Extension Phase:	

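### A SOC oral bridging stop date that is year-only or missing is not bounded by resumed CAB/RPV dosing, so bridging exposure can be overstated and CAB+RPV exposure understated by the same days

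*SAP*

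**What the plan says.** All references are to the current RAP text (Amendment 1) unless stated.

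- **Imputation rule (13.7.2.1, ART Medications).** "If the partial date is a stop date, a '28/29/30/31' will be used for the day"; the same sentence continues "dependent on the month and year) and 'Dec' will be used for the month". A completely missing stop is treated as ongoing unless the record sits on the PRIOR ART form.
- **Only cap.** For the PRIOR ART form the stop is "min (imputed stop date, Intervention phase treatment start date - 1"). No bound is stated for ART taken on study. SOC oral bridging is such ART: Listing 34 (Concomitant ART Medications) carries a yes/no column for it.
- **Exposure (13.6.4).** SOC bridging exposure is "Duration of the SOC ART medication taken as oral bridging during the Intervention Phase". It is subtracted from overall exposure to give CAB+RPV exposure and, for Intervention plus Extension, IP exposure.
- **Treatment state (13.4.2, Table 10).** On-treatment ends at the later of last injection + 35 days and "Date of Last Dose of Oral Study Treatment (CAB+RPV or SOC Bridging) +1". Note b applies this limit only to participants who permanently discontinued study treatment.
- **LTFU day (13.6.1).** The origin is "the end of IP treatment [i.e. max(Last IM Injection Date, Last Oral Bridging End Date").
- **Adherence (13.6.2).** Missed injections are classed as with or without oral bridging. "Missed injections occurring during periods of on-going oral bridging" are not counted as expected.

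**The concern.** A bridging period ends when the participant goes back to study injections or oral CAB+RPV, or leaves study treatment. The imputation rule uses none of these dates. A short bridging whose stop is known only to the year, or not at all, therefore continues on paper through months in which the participant was receiving injections. Because CAB+RPV exposure is obtained by subtraction, each day wrongly added to bridging is taken from CAB+RPV. The same end date also enters the on-treatment limit and the LTFU day origin.

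The SAP uses the missing device elsewhere. PRIOR ART stops are bounded with a minimum, and so are partial injection-site-reaction start dates in months with oral bridging. The Non-ART rows treat a missing end day and a missing end day and month as separate cases; the ART bullet merges them.

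**Working it through.** The SAP gives no figure to reproduce, so its date rules are applied to an illustrative participant.

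**Assumed dates (not in the SAP).** First oral dose 15 August 2019; Month 13 visit 14 September 2020; latest visit and data cut-off 14 March 2021; true SOC bridging 1 to 15 April 2020 (15 days); injections then resumed and treatment continued.

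**Formulas (13.6.4).**
- Overall exposure for a participant still on treatment = latest visit in scope − first oral dose + 1.
- Bridging = min(bridging stop, end of scope) − bridging start + 1. For the Intervention Phase the scope ends on 13 September 2020, the day before Month 13.
- CAB+RPV (or IP) exposure = overall exposure − SOC bridging.

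**Overall exposure.** Intervention Phase: 15 August 2019 to 14 September 2020 = 397 days. Intervention + Extension: to 14 March 2021 = 578 days.

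| Recorded stop | Stop used | Bridging, Intervention | CAB+RPV of 397 | Bridging, Int. + Ext. | IP exposure of 578 |
|---|---|---|---|---|---|
| 15 Apr 2020 (truth) | 15 Apr 2020 | 15 | 382 | 15 | 563 |
| Apr 2020, month kept | 30 Apr 2020 | 30 | 367 | 30 | 548 |
| 2020 only | 31 Dec 2020 | 166 | 231 | 275 | 303 |
| Missing | ongoing | 166 | 231 | 348 | 230 |

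For the year-only stop in the Intervention Phase, 1 April to 13 September is 30 + 31 + 30 + 31 + 31 + 13 = 166 days. The excess is 166 − 15 = 151 days, or 151/397 = 38% of that participant's overall exposure. If all 115 planned participants had 397 days, the total would be 115 × 397 = 45,655 days, and one such record would move it by 151/45,655 = 0.3%.

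**On-treatment end (permanent discontinuers only).** Same true bridging, stop recorded as 2020, so imputed stop + 1 = 1 January 2021.

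| Last injection | + 35 days | Shift of on-treatment end |
|---|---|---|
| 7 May 2020 | 11 June 2020 | 204 days |
| 7 Sep 2020 | 12 Oct 2020 | 81 days |
| 14 Nov 2020 | 19 Dec 2020 | 13 days |
| 27 Nov 2020 | 1 Jan 2021 | 0 |

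These shifts assume no earlier LTFU ART start. If the recorded month is kept, the shift is 0 in all four cases.

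**LTFU day.** Suppose bridging was the last treatment, truly ended on 14 May 2020, and a long-term follow-up visit fell on 12 August 2020. LTFU day = 90 + 1 = 91, which lies in the Month 3 window of Table 5. With an end date of 31 December it is −141 + 1 = −140. Table 5 starts at Day 1, so the visit falls in no window.

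**Adherence.** Expected injections run from Month 2 to the nominal month of the last injection visit. An injection missed between the true end of bridging and a later injection stays expected; only its with/without-bridging label can change.

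**The case against.** The strongest reply is that the gap is narrow and mostly contained.

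- **A recorded month is probably kept.** The day depends on the month and year, which makes sense only if a known month is retained. A reader might infer that every partial ART stop goes to December; the text does not establish that. A day-only gap then adds at most 30 days. This stands, although the bullet should say so.
- **Other limits exist.** Exposure stops at the phase end and the latest visit. Snapshot step 3.2.1 takes the minimum with LTFU ART start, and phase assignment makes data after that start post-treatment. This stands too, except that when the LTFU ART start date is missing the phase tables apply only the lower bound.
- **On-treatment status.** A reader might infer that participants who resumed injections gain on-treatment time. Table 10 note b rules this out for those still on treatment.
- **Adherence denominator.** A reader might infer that missed injections drop out of it. Visits after the last injection were never expected. The exclusion for ongoing bridging, judging by its own two examples, concerns bridging that no injection follows.
- **Use of imputed dates is inferred.** The current text allows imputation for phase slotting or specific analysis purposes and does not name exposure. The earlier RAP barred imputed dates from durations. Dropping that sentence is not itself an error, but the current plan neither directs nor prevents the use.
- **The trigger is unlikely.** Dose interruptions are discussed with the medical monitor, bridging records are listed, and cleaning precedes database freeze. The study is descriptive, with no hypothesis test.

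These points limit the frequency and reach of the problem. None bounds a year-only or missing bridging stop at the next study dose.

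**Conclusion.** The point holds in limited form. A SOC bridging stop known only to the year, or missing, is not bounded by resumed CAB/RPV dosing. If such a record occurs and its imputed date enters exposure, bridging is too long and CAB+RPV or IP exposure too short by the same number of days. In the illustration that is 151 of 397 days for one participant and about 0.3% of the total.

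For permanent discontinuers the on-treatment end is late only when the imputed stop + 1 passes last injection + 35 and no LTFU ART start comes earlier. Their LTFU day origin can also shift. For participants who resumed injections, the most that changes in the adherence analysis is a label.

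The sizes rest on assumed dates. The SAP gives no count of incomplete bridging stops, and the number is probably small. This is a low-cost correction to a rule that gives a wrong answer when triggered; it does not threaten the study's conclusions.

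**What to change.** Amend 13.7.2.1, ART Medications. This concerns data handling only and changes no clinical rule.

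1. If only the day of a stop date is missing, keep the recorded month and use its last day.
2. For on-study SOC oral bridging with a missing day, a missing day and month, or a completely missing stop, set the stop to the earliest of: the imputed date (if any); the day before the next CAB/RPV injection or oral CAB+RPV dose; the study treatment discontinuation date; the day before LTFU ART start; and the data cut-off.
3. State whether imputed dates enter exposure durations.

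The cost is a few sentences and one minimum in the dataset program. All bounding dates come from dosing, disposition and medication records that the SAP's own derivations already use, so no new data are needed.
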